# **Protocol Amendment Summary of Changes Table**

Document History	Document History				
Document	Version Date	Summary and Rationale for Changes			
Protocol amendment 2	03 May 2021	
 
As more data about COVID-19 continue to accrue, the potential duration of protection afforded after a wild-type SARS-CoV-2 infection, and by vaccination, remains unknown. If a third dose of BNT162b2 becomes necessary, whether it be with the current vaccine or one encoding for a variant of concern (VOC), it will be important to understand the safety and immunogenicity when the third dose is administered in close proximity to the second dose. Therefore, in order to describe the safety and heterologous/homologous protection against emerging VOC(s), an additional dose of BNT162b2 or BNT162b2.B.1.351 will be given to 60 participants, 18 through 50 years of age, approximately 3 months after their second dose of BNT162b2. Safety and immunogenicity will be assessed up to 1 month after the additional dose.
 
Updates were made to Section 2.3.1 (Risk Assessment) for the risk of COVID-19 disease enhancement as a theoretical risk based on the results from studies in the program to date.
 
In the primary study, the endpoint for the lot-comparison analyses is now confirmed to be the full-length S-binding IgG levels. This is the assay selected for new studies in the program.
 
CCI
 
Various updates and minor corrections were made throughout the document, including Sections 2 and 9.
 
			
Protocol amendment 1	26 January 2021	With the demand to vaccinate the general population and the Phase 1 data showing robust immunogenicity at			
		a 20-μg dose in the younger population, a noninferiority analysis of a 20-μg dose compared with the standard 30-μg dose has been added. The endpoint for this analysis is SARS-CoV-2 neutralizing titers.			
		• In the event that the 20-μg dose is found to be suboptimal, the provision to administer a single 30-μg			
		
 
dose outside the study has been added.
 
The study intervention arm "control lot" has been removed.
 
			
		
 
The study population age range has changed from 18 through 55 years to 12 through 50 years.
 
Stratification by age group has been added to allow for balanced age representation across all arms.
 
			

T		D 04 112 0 2 104 1
		
 
Because of the addition of participants 12 through 17 years of age, multisystem inflammatory syndrome in children is added as an AE of special interest.
 
Added the possibility of assessing S1-binding instead of
 

		the full-length S-binding IgG levels.
		
 
Because of an increased incidence rate of SARS-CoV-2 in the US, it is expected that more participants will be diagnosed with COVID-19 during their time in the study; therefore, the nonevaluable rate was increased from 15% to 20%.
 

		The criterion to discontinue the study intervention at Dose 2 in participants who were diagnosed with COVID-19 between Visit 1 and Visit 2 has been removed, as the ACIP recommends that vaccination should be offered to persons regardless of history of prior symptomatic or asymptomatic SARS-CoV-2
		infection.
		• The exclusion criterion for immunocompromised individuals was inadvertently omitted and now appears as exclusion criterion 5.
		
 
The Benefit/Risk Assessment section has been updated to reflect the additional clinical data available for BNT162b2. The Overall Benefit/Risk Conclusions section has not changed.
 

		• A clarification was made in Section 8.1.1, Biological
		Samples, that no testing of the participant's DNA will be performed.
Original protocol	24 Nov 2020	N/A

This amendment incorporates all revisions to date, including amendments made at the request of country health authorities and IRBs/ECs.

#### 1. PROTOCOL SUMMARY

# 1.1. Synopsis

**Short Title:** A Phase 3 Study to Evaluate the Safety, Tolerability, and Immunogenicity of Multiple Production Lots and Dose Levels of BNT162b2 RNA-Based COVID-19 Vaccines Against COVID-19 in Healthy Participants

#### Rationale

A pneumonia of unknown cause detected in Wuhan, China, was first reported in December 2019. In January 2020, the pathogen causing this outbreak was identified as a novel coronavirus 2019. The outbreak was declared a Public Health Emergency of International Concern on 30 January 2020. On 12 February 2020, the virus was officially named as severe acute respiratory syndrome coronavirus 2 (SARS-CoV-2), and the WHO officially named the disease caused by SARS-CoV-2 as coronavirus disease 2019 (COVID-19). On 11 March 2020, the WHO upgraded the status of the COVID-19 outbreak from epidemic to pandemic, which is now spreading globally at high speed.

Based on Phase 2/3 safety, immunogenicity, and efficacy data, BNT162b2 was shown to be effective and has been authorized for temporary or emergency use in multiple countries.

BNT162b2 is administered intramuscularly as a 2-dose series spaced 21 days apart at a dose of 30 μg each. Study C4591001 (NCT04368728) is an ongoing Phase 1/2/3 trial designed to generate safety, tolerability, immunogenicity, and efficacy data from a novel RNA-based vaccine candidate. The trial is being conducted in a heterogeneous study population: eligible participants ≥12 years of age, healthy participants, including those participants with stable chronic medical conditions, as well as HIV-, HCV-, and HBV-positive participants. BNT162b2 was selected from the Phase 1 part of this study based on the overall safety, tolerability, and immunogenicity.

To support distribution of this vaccine on a wider scale, the study will evaluate the immune response across 4 different BNT162b2 lots manufactured at a commercial scale: 3 lots of drug substance manufactured in the United States and 1 lot of drug substance manufactured in Europe (Arms 1-4) and describe the safety and tolerability of these different vaccine lots in healthy participants.

While the 30-µg dose was selected based on favorable reactogenicity and immunogenicity in both younger and older participants, Phase 1 immunogenicity and safety data were also robust with the 20-µg dose in the younger population. Investigating the noninferiority of a 20-µg dose compared with the standard 30-µg dose may support the potential use of a lower vaccine dose in the defined population of this study. This will be of value with the demand to vaccinate the general population. Therefore, a noninferiority analysis will be performed in this study of a 20-µg dose against the standard 30-µg dose. The 20-µg dose arm (Arm 5) will contain the same US-manufactured drug substance as one of the US lots in the study and will be compared against that same lot in the noninferiority analysis.

Note: In this protocol, the US-manufactured drug substance lots are also referred to as the "US lots" and the EU-manufactured drug substance lot is also referred to as the "EU lot."

In light of the unknowns regarding duration of protection, as well as the emerging variants of concern (VOCs), it is important to understand the boostability of BNT162b2, and potential heterologous protection against emerging VOC(s). To this end, a booster study extension has been added in protocol amendment 2 in which a small subset of adult participants who received Doses 1 and 2 at 30  $\mu g$  from a designated US lot(s) will receive a single dose of either 30  $\mu g$  BNT162b2 or 30  $\mu g$  BNT162b2.B.1.351 (BNT162b2s01 vaccine encoding for the full-length spike protein of South Africa variant B.1.351 [formerly known as BNT162b2sA]). This third dose will be administered at approximately 3 months after Dose 2 of BNT162b2.

# **Primary Study**

# Objectives, Estimands, and Endpoints

Objectives	Estimands	Endpoints			
Primary Immunogenicity – Lot Comparisons					
To demonstrate that the immune responses induced by BNT162b2 are similar across the 3 US lots (Arms 1, 2, and 3) in participants without evidence of SARS-CoV-2 infection during the study.	In participants complying with the key protocol criteria (evaluable participants):  • GMR from one US lot to another lot (Arm 1/Arm 2, Arm 1/Arm 3, and Arm 2/Arm 3) 1 month after Dose 2	Full-length S-binding IgG levels			
To demonstrate that the immune response induced by the EU lot (Arm 4) of BNT162b2 is similar to the pooled US lots (Arms 1, 2, and 3) in participants without evidence of SARS-CoV-2 infection during the study.	In participants complying with the key protocol criteria (evaluable participants):  • GMR from the EU lot (Arm 4) to the pooled US lots (Arm 4/pooled Arms 1, 2, and 3) 1 month after Dose 2	Full-length S-binding IgG levels			
Prin	nary Immunogenicity – Dose Comp	arison			
To demonstrate the noninferiority of the immune response to prophylactic BNT162b2 in participants receiving 20 µg compared to participants receiving the standard 30-µg dose (prepared from the same manufacturing lot) without evidence of SARS-CoV-2 infection during the study.	In participants complying with the key protocol criteria (evaluable participants):  • GMR, estimated by the ratio of the geometric mean of SARS-CoV-2 neutralizing titers in the 2 dose groups 1 month after Dose 2	SARS-CoV-2 neutralizing titers			
	Primary Safety				
To evaluate the safety of BNT162b2 when administered on a 2-dose schedule in healthy participants 12 through 50 years of age.	In participants receiving at least 1 dose of study intervention from each vaccine group (individual and pooled US lots, EU lot, 20-µg dose), the percentage of participants reporting:  • Local reactions for up to 7 days following each dose  • Systemic events for up to 7 days following each dose  • AEs and SAEs from Dose 1 to 1 month after Dose 2	Local reactions (pain at the injection site, redness, and swelling)     Systemic events (fever, fatigue, headache, chills, vomiting, diarrhea, new or worsened muscle pain, and new or worsened joint pain)     AEs     SAEs			

# PF-07302048 (BNT162b2 RNA-Based COVID-19 Vaccine) Protocol C4591017 Final Protocol Amendment 2, 03 May 2021

Secondary Immunogenicity					
To describe the immune responses induced by different 30-µg dose manufacturing lots of BNT162b2.	In evaluable participants from each vaccine group (individual and pooled US lots, EU lot):  GMCs at baseline (before Dose 1) and 1 month after Dose 2  GMFR from baseline (before Dose 1) to 1 month after Dose 2	Full-length S-binding IgG levels			
To describe the immune responses induced by different doses of BNT162b2.	In evaluable participants from each vaccine group (20 μg and 30 μg from the same US lot):  GMCs at baseline (before Dose 1) and 1 month after Dose 2  GMFR from baseline (before Dose 1) to 1 month after Dose 2	SARS-CoV-2 neutralizing titers			

Note: "US lots" refers to the lots of study vaccine containing drug substance manufactured in the United States. "EU lot" refers to the lot of study vaccine containing drug substance manufactured in Europe.

# **Booster Study**

Estimands	Endpoints			
Primary Safety				

 
In participants receiving the third dose of study intervention, the percentage of participants reporting:
 
Local reactions for up to 7 days following the booster dose
 
Systemic events for up to 7 days following the booster dose
 
AEs and SAEs from the booster dose to 1 month after the booster dose
 
	Local reactions (pain at the injection site, redness, and swelling)     Systemic events (fever, fatigue, headache, chills, vomiting, diarrhea, new or worsened muscle pain, and new or worsened joint pain)     AEs     SAEs			
Primary Immunogenicity				

 
In evaluable participants from each vaccine group (either BNT162b2 30 μg or BNT162b2.B.1.351 30 μg):
 
Geometric mean neutralizing titers at baseline (before Dose 1), 1 month after Dose 2, before Dose 3, and 1 week after and 1 month after Dose 3
 
Geometric mean IgG concentrations at baseline (before Dose 1), 1 month after Dose 2, before Dose 3, and 1 week after and 1 month after Dose 3
 
GMFRs from 1 month after Dose 2 to 1 week after and 1 month after Dose 3 and from before Dose 3 to 1 week after and 1 month after Dose 3
 
The percentages of participants with seroresponse§ (based on neutralizing titers) to the reference strain at 1 month after Dose 3
 
The percentages of participants with seroresponse§ (based on neutralizing titers) to the reference strain at 1 month after Dose 3
 
The percentages of participants with seroresponse§ (based on neutralizing titers) to the B.1.351 variant strain at 1 month after Dose 2, before Dose 3, and 1 week
 
	
 
SARS-CoV-2 reference-strain neutralizing titer†
 
SARS-CoV-2 B.1.351-strain neutralizing titer††
 
Full-length S-binding IgG levels
 
			
	Primary Safety  In participants receiving the third dose of study intervention, the percentage of participants reporting:  • Local reactions for up to 7 days following the booster dose • Systemic events for up to 7 days following the booster dose • AEs and SAEs from the booster dose to 1 month after the booster dose  Primary Immunogenicity  In evaluable participants from each vaccine group (either BNT162b2 30 μg or BNT162b2.B.1.351 30 μg): • Geometric mean neutralizing titers at baseline (before Dose 1), 1 month after Dose 2, before Dose 3, and 1 week after and 1 month after Dose 3 • Geometric mean IgG concentrations at baseline (before Dose 1), 1 month after Dose 2, before Dose 3, and 1 week after and 1 month after Dose 3 • GMFRs from 1 month after Dose 2 to 1 week after and 1 month after Dose 3 and from before Dose 3 to 1 week after and 1 month after Dose 3 • The percentages of participants with seroresponse (based on neutralizing titers) to the reference strain at 1 month after Dose 3 • The percentages of participants with seroresponse (based on neutralizing titers) to the Reference strain at 1 month after Dose 3 • The percentages of participants with seroresponse (based on neutralizing titers) to the B.1.351 variant strain at 1 month after			

\* BNT162.B.1.351 = BNT162b2s01 vaccine encoding for the full-length spike protein of South African—origin variant B.1.351 (formerly BNT162b2sA).

† SARS-CoV-2 reference-strain neutralizing titers = neutralizing titers against SARS-CoV-2 USA-WA1/2020 virus. †† SARS-CoV-2 B.1.351-strain neutralizing titers = neutralizing titers against SARS-CoV-2 virus with B.1.351 spike. § Seroresponse is defined as ≥4-fold increase from baseline (before Dose 1) to the specified time point. If the baseline measurement is below LLOQ, a postvaccination measurement of ≥4 × LLOQ is considered a seroresponse.

# **Overall Design**

This is a Phase 3, randomized, observer-blind study to evaluate the safety, tolerability, and immunogenicity of 4 manufacturing lots of BNT162b2 as a 30-µg dose and an additional 20-µg dose arm using one of the same manufactured 30-µg lots. BNT162b2 is an RNA-based COVID-19 vaccine, administered on a 2-dose schedule in healthy participants 12 through 50 years of age. Participants will be randomized to 1 of 5 arms in a 2:2:2:1:2 ratio (Arm 1: Arm 2: Arm 3: Arm 4: Arm 5), where Arms 1, 2, and 3 contain US-manufactured drug substance for 30-µg dosing; Arm 4 contains EU-manufactured drug substance for 30-µg dosing. In order to allow for balanced age representation across all arms, the randomization will be stratified by age groups: 12 through 17, 18 through 30, and 31 through 50 years.

The duration of the study for each participant will be approximately 2 months. The study will be conducted in the United States.

Protocol amendment 2 has added a booster study in which a subset of the adult participants (18 through 50 years of age) who each received two 30-µg doses of the designated US lot(s) will be randomly assigned to 1 of 2 arms in a 1:1 ratio (Booster 1: Booster 2), where Booster 1 is BNT162b2 at 30 µg and Booster 2 is BNT162b2.B.1.351 at 30 µg. The third dose will be administered approximately 3 months after BNT162b2 Dose 2 of the primary study.

The duration of the booster study for each participant will be approximately 1 month. This study is observer-blinded, to minimize changes in study conduct compared with the primary study.

#### **Number of Participants**

Approximately 340 participants will be randomly assigned to each of the 3 US lots (Arms 1-3) and to the 20-µg arm (Arm 5) and approximately 170 participants will be randomly assigned to the EU lot (Arm 4), for a total of approximately 1530 randomized participants. It is expected that approximately 1224 evaluable participants will complete the study, based on a 20% nonevaluable rate.

In the booster study, approximately 30 participants will be assigned to each arm for a total of 60 participants to be enrolled. It is expected that approximately 48 evaluable participants will complete the study, based on a 20% nonevaluable rate.

# Data Monitoring Committee or Other Independent Oversight Committee

This study will use a DMC. The DMC is independent of the study team and includes external members. The DMC charter describes the role of the DMC in more detail.

The DMC will be responsible for ongoing monitoring of the safety of participants in the study according to the charter. This may include, but is not limited to:

- Contemporaneous review of related AEs up to 1 month after completion of the vaccination schedule,
- Contemporaneous review of all SAEs up to 1 month after completion of the vaccination schedule.

The recommendations made by the DMC to alter the conduct of the study will be forwarded to the appropriate Pfizer personnel for final decision. Pfizer will forward such decisions, which may include summaries of aggregate analyses of safety data, to regulatory authorities, as appropriate.

#### **Statistical Methods**

There are 2 primary immunogenicity objectives on manufacturing lot comparisons. The first primary immunogenicity objective will be evaluated by formal hypothesis tests for consistency of the immune response induced by BNT162b2 30 µg across the 3 US lots. GMRs of the full-length S-binding IgG levels and their 2-sided 95% CIs will be provided for each pair of between-lot comparisons (Arm 1 to Arm 2, Arm 1 to Arm 3, and Arm 2 to Arm 3) using a 1.5-fold equivalence margin. Two lots will be considered similar if the 2-sided 95% CI for the GMR is contained in the interval (0.67, 1.5). Overall, the lots will be considered similar if the 1.5-fold equivalence criterion is met for all 3 between-lot comparisons (Arm 1 to Arm 2, Arm 1 to Arm 3, and Arm 2 to Arm 3).

The second primary immunogenicity objective of similarity between the EU lot and the 3 pooled US lots will be assessed sequentially after the first primary objective is met. Using a 1.5-fold equivalence margin, the EU lot and the pooled US lots will be considered similar if the 2-sided 95% CI for the GMR of the full-length S-binding IgG levels is contained in the interval (0.67, 1.5).

The primary immunogenicity objective of noninferiority of the BNT162b2 20-µg vs 30-µg dose levels, using a 1.5-fold noninferiority margin, will be achieved if the lower limit of the 2-sided 95% CI for the GMR of the SARS-CoV-2 neutralizing titers is >0.67.

With 270 evaluable participants per US lot, the study has a power of 91.7% for considering the 3 US lots to be similar. The study will also provide 92.8% power for considering the EU lot similar to the US lots, with 135 evaluable participants in the EU lot and 810 evaluable participants in the pooled US lots. With 270 evaluable participants for the 20-µg and 30-µg dose groups (Arm 5 and the corresponding US 30-µg lot [Arm 1, 2, or 3]), the study will have a power of 94.7% for declaring noninferiority. Assuming a nonevaluable rate of 20%, the study will randomize approximately 340 participants in each US lot, 170 participants in the EU lot, and 340 participants in the 20-µg dose group to achieve the required evaluable participants.

The secondary immunogenicity objectives will be evaluated descriptively by GMCs, GMFRs, and the associated 95% CIs for the full-length S-binding IgG levels for Arms 1

through 4 and GMTs, GMFRs, and the associated 95% CIs for the SARS-CoV-2 neutralizing titers for Arm 5 and the corresponding US 30-µg lot (Arm 1, 2, or 3).

[figure not shown]
The primary safety objective will be evaluated by descriptive statistics including counts and percentages of participants and the associated Clopper-Pearson 95% CIs for local reactions, systemic events, and AEs/SAEs, for each vaccine group.

In the booster study, the primary immunogenicity objectives will be evaluated descriptively by GMCs, GMFRs, and the associated 95% CIs for the full-length S-binding IgG levels and by GMTs, GMFRs, and the associated 95% CIs for the SARS-CoV-2 neutralizing titers for both the reference strain and the B.1.351 strain for each vaccine group. Additionally, the percentage of participants with a seroresponse to the reference strain and B.1.351 strain using neutralizing titers will be summarized.

The primary safety objective will be evaluated by descriptive statistics including counts and percentages of participants and the associated Clopper-Pearson 95% CIs for local reactions, systemic events, and AEs/SAEs, for each vaccine group.

[figure not shown]

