# 9.2. Sample Size Determination

# **Primary Study**

[figure not shown]
The study sample size is based on the lot-to-lot similarity evaluation for the first and second primary immunogenicity endpoints, full-length S-binding IgG levels 1 month after Dose 2, using a 1.5-fold equivalence margin for each between-lot comparison across 3 US lots (Arms 1-3) and the comparison of the EU lot (Arm 4) to the US lots.

With 270 evaluable participants per US lot (Arms 1-3), and the stated assumptions on the maximum between-lot difference and the standard deviation, the study has a power of 91.7% for considering the 3 US lots to be similar. The study will also provide 92.8% power for considering the EU lot (Arm 4) similar to the US lots, with 135 evaluable participants in the EU lot (Arm 4) and 810 evaluable participants in the pooled US lots (Arms 1-3)

With 270 evaluable participants each in the 20-µg dose group and corresponding 30-µg dose group, and assumptions on the standard deviation SARS-CoV-2 neutralizing titers (on the natural log scale) between the 2 dose groups, the study has 94.7% power to declare noninferiority of 20 µg to 30 µg

Assuming a nonevaluable rate of 20%, the study will randomize approximately 340 participants in each US lot (Arms 1-3), 170 participants in the EU lot (Arm 4), and 340 participants in the 20-μg dose group (Arm 5) to achieve the required evaluable participants.

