1. VERSION HISTORY

Table 1. Summary of Changes

Version/ Date	Associated Protocol Amendment	Rationale	Specific Changes
1/ 17 Feb 2021	1 26 Jan 2021	N/A	N/A
2/ 06 May 2021	2 03 May 2021	Protocol amendment 2 and BDR team review	
 1. Booster study-related information added. 2. Removed “S1-binding IgG” throughout the document, as “full-length S-binding IgG” assay is the chosen assay for this protocol. 3. “Equivalence” is replaced with “similarity” for statistical comparisons. 4. Removed “by day” e-diary figures.
3/ 15 Oct 2021	2 03 May 2021	CCI [REDACTED]	
 1. Revised Section 5.1.2 to sequentially evaluate the 3 primary objectives. 2. Revised Section 7 to indicate 2 separate analyses will be performed.

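### The stated 92.8% power for the EU-lot claim is for that comparison alone; behind the Protocol's own US-lot gate (91.7%) it is about 85%

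*Protocol*

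**What the plan says.** The first primary objective is similarity of the three US lots. The synopsis sets an all-pairs rule for it: "Overall, the lots will be considered similar if the 1.5-fold equivalence criterion is met for all 3 between-lot comparisons". Its power is given as follows: "With 270 evaluable participants per US lot, the study has a power of 91.7% for considering the 3 US lots to be similar".

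The second primary objective, EU lot against pooled US lots, "will be assessed sequentially after the first primary objective is met". The synopsis nevertheless says: "The study will also provide 92.8% power for considering the EU lot similar to the US lots". The evaluable numbers are 135 and 810.

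Section 9.2 gives the same pair of figures: "the study has a power of 91.7% for considering the 3 US lots to be similar", and "The study will also provide 92.8% power for considering the EU lot (Arm 4) similar to the US lots". It also makes both comparisons part of the justification for the trial's size: "The study sample size is based on the lot-to-lot similarity evaluation for the first and second primary immunogenicity endpoints".

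The 20-µg noninferiority objective is stated to have 94.7% power. The SAP version history records for version 3: "Revised Section 5.1.2 to sequentially evaluate the 3 primary objectives". The revised Section 5.1.2 is redacted, so the order is not visible.

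**The concern.** The synopsis sets a gate with 91.7% power and then credits the claim behind that gate with 92.8%. No visible sentence says that the second figure ignores the gate, and none gives a power for passing both steps.

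A reader would take the risk of not obtaining the EU-lot claim to be about 7 in 100. That claim carries weight: Section 2.1 presents support for both the US and the EU manufacturing processes at commercial scale as an aim of the study. Someone wanting the stated power might also think of enlarging Arm 4, but that alone could never deliver it, because the gate caps the claim at 91.7% whatever the size of the EU arm.

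**Working it through.** **Inputs.** From the synopsis and Section 9.2: US-lot power p1 = 0.917 (270 evaluable per lot); EU-lot power p2 = 0.928 (135 vs 810); dose-comparison power p3 = 0.947 (270 vs 270). The margin is 1.5-fold with 2-sided 95% CIs. The standard deviation (SD) and the assumed lot differences are redacted, so the values used below are assumptions.

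**1. The plan's own figure.** Neither 91.7% nor 92.8% can be reproduced independently without the redacted inputs, but both are credible as single-objective powers. For the EU comparison, with m = ln(1.5) = 0.4055:

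- power = Φ((m − d)/se − 1.96) − Φ((−m − d)/se + 1.96)
- se = SD × √(1/135 + 1/810) = 0.0930 × SD

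Assume a true EU ratio of 1.05 (d = 0.0488) and an SD of 1.103 on the natural-log scale. Then se = 0.1026, and power = Φ(1.52) − Φ(−2.47) = 0.935 − 0.007 = 0.929. With the same SD and one US lot shifted 1.05-fold, simulation gives 0.917 for the three-pair US objective. Other pairs of SD and lot difference fit equally well.

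**2. Ceiling.** P(US lots pass and EU lot passes) ≤ P(US lots pass) = 0.917, which is below 0.928. So 92.8% cannot be power through the gate.

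**3. Dependence between the two results.** Let the pooled US mean be weighted by participants, with N US participants in all and common variance s². For any two US lots i and j:

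Cov(mean_i − mean_j, pooled US mean) = s²/N − s²/N = 0.

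Arm 4 is a separate sample. Under the normal model the US contrasts are therefore independent of the EU-minus-pooled contrast, even with unequal arm sizes. A shared SD estimate adds negligible dependence.

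**4. Power through the gate.** 0.917 x 0.928 = 0.851. The failure risk is 1 − 0.851 = 14.9%, against 1 − 0.928 = 7.2%.

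**5. Simulation check.** Four arm means were drawn 400,000 times per scenario. Assumed maximum US-lot ratios ran from 1.00 to 1.25 in two lot patterns. SDs (0.58 to 1.15) and EU ratios were back-solved to the two stated powers. Joint power was 0.851 to 0.852 in every scenario. In a further set with evaluable US arms of 255, 270 and 285, it was 0.847 to 0.853.

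**6. Limits with no independence assumption.** Lower: 0.917 + 0.928 − 1 = 0.845. Upper: 0.917. The range still excludes 92.8%.

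**7. If the dose objective is also in the chain (SAP version 3).**

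| Position | Product | Limits |
|---|---|---|
| Dose first or ungated | 94.7% | not applicable |
| Dose second, after US lots | 0.917 x 0.947 = 86.8% | 0.917 + 0.947 − 1 = 86.4% to 91.7% |
| Dose last, after US and EU | 0.917 x 0.928 x 0.947 = 80.6% | 0.851 + 0.947 − 1 = 79.8% to 85.1% |
| EU last, after US and dose | 80.6% | 79.8% to 85.1% |

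The products involving the dose test assume independence, which step 3 does not establish for that test. The limits in the last two rows use only the US–EU independence from step 3. With no independence at all they widen to 0.917 + 0.928 + 0.947 − 2 = 79.2% at the lower end and 91.7% at the upper.

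**The case against.** The strongest reply is that no stated number is wrong. Each power is tied to its own comparison and its own sample size, per-comparison power is a common way to report, and a careful reader can see that 92.8% exceeds 91.7% and draw the conclusion. This stands as far as it goes: the individual calculations are not disputed. But the gate and the unlabelled figure are in the same section, and the sentence speaks of what the study will provide.

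A second reply is redaction. Table 4, parts of Section 9.2 and SAP Section 5.1.2 are blacked out and may hold a power for the whole sequence. That is possible, and the absence of visible text is not itself a fault. The synopsis passage is complete, however, and nothing elsewhere can make 92.8% attainable through a 91.7% gate.

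Third, SAP version 3 postdates the Protocol, so 85% may not describe the current order. This is right, and it is why 85% is tied here to the order in the Protocol. It is also fair that the dose-test products are only indicative: SAP Section 6.1.1.3.1 compares Arm 5 with Arm 1, which also enters the US-lot test, and the correlation between IgG and neutralizing titers is unknown.

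Finally, the consequence is limited. Type I error, estimates and decision rules are untouched, no target power is stated, and the EU ratio with its interval is planned for reporting without any condition on the gate (Protocol Section 9.4.2, SAP Section 6.1.1.2.1). If the gate fails, the formal claim is lost but the estimate is still available.

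**Conclusion.** The concern holds. As the Protocol reads, the power to obtain the EU-lot claim is about 85%, not 92.8%, and it could not exceed 91.7% under any dependence between the two tests. The 85% rests on the two stated powers, the stated gate and the independence that follows from the design; it does not depend on the redacted SD or lot differences. For the 20-µg claim, the visible text supports only a range by testing order: 94.7% if first or ungated, about 87% if second after the US lots, about 81% if last. This is a fault in how the power is stated. It does not show that the sample size is wrong.

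**What to change.** In the synopsis and in Section 9.2, label 91.7%, 92.8% and 94.7% as the power of each comparison on its own. Next to them, state the power under the testing order in force: about 85% for the EU lot behind the US-lot gate as the Protocol now reads, with the remaining figures computed by the sponsor from the SAP version 3 sequence and its own planning assumptions. If a sequence power already exists in redacted text, it only needs to be carried into these two places.

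The cost is wording. Sample size, margins and tests do not change. The one drawback is that the stated power looks less favourable.
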